University of Kansas Medical Center RESEARCH PROTOCOL INVOLVING HUMAN SUBJECTS TEMPLATE WITH GUIDANCE

Version date: 8/11/2015

Principal Investigator: [name].

Study Title: Impact of Rifaximin Therapy on Intestinal Byproducts in Chronic Kidney Disease

Co- Investigator(s): [name], D.O.

[name], M.B., BChir [name]. [name] [name] [name]

(NOTE: not all sections of this template will apply to all projects. "N/A" is an acceptable response.)

I. Purpose, Background and Rationale

A. Aim and Hypotheses

1. Begin with a brief introduction to describe the origin and importance of the study.

Trimethylamine-N-oxide (TMAO) is a circulating organic compound produced by the metabolism of dietary L-carnitine and choline. TMAO was recently identified to directly induce atherosclerosis in rodents and is strongly associated with the incidence of cardiovascular events in humans. The proposed investigation is a prospective pilot study to assess the impact of alterations in the intestinal flora by short-term antibiotic suppression (with Rifaximin) and to measure its effect on serum TMAO levels in patients with advanced-stage (stage IV-V) chronic kidney disease.

2. Clearly state the aim(s) and hypothesis(es), listing them by number if there is more than one.

Hypothesis: Treatment of CKD patients with Rifaximin will suppress the bacterial flora that are responsible for the generation of trimethylamine, a TMAO precursor, and subsequently reduce serum TMAO concentrations.

Primary Aim:

 The primary outcome of interest will be the change in serum TMAO concentrations (post-therapy minus pre-therapy TMAO) following Rifaximin administration for 10 days.

Secondary Aims:

- 1. To measure the change in urine TMAO
- 2. To measure the change in serum endotoxin, IL-6, IL-8, TNF-alpha levels
- 3. To measure the alteration of bowel microbiota
- 4. To assess the above changes in steady state, 2 weeks after completion of therapy

B. Background and Significance

1. Study Significance: what the proposed research is intended to accomplish and the importance of the results

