- In a second cross-sectional investigation we evaluated TMAO levels compared with prevalent coronary artery atherosclerosis in a subset of subjects with chronic kidney disease undergoing coronary angiography (n=220). We noted a significant correlation between serum TMAO and coronary atherosclerosis burden quantified by modified Gensini scoring (r=0.15, P=0.03 by Spearman correlation). After multivariable adjustment for traditional cardiovascular risk factors the correlation remained significant (P=0.048).

C. Rationale

1. Explain how the background information from the literature supports the current proposed hypothesis(es).

It is a known phenomenon that patients diagnosed with chronic kidney disease (CKD) exhibit a high prevalence of cardiovascular disease which largely accounts for the remarkably high mortality in this group. The average 5-year survival for patients receiving chronic dialysis therapy is approximately 35%, with >50% of this mortality resulting directly from cardiovascular causes (1). It is apparent that patients with chronic kidney disease experience an increased burden of atherosclerosis compared to matched individuals with normal kidney function. The presence of traditional risk factors for the development of atherosclerosis, such as diabetes, smoking and hypertension, do not fully account for the accelerated atherosclerosis observed in CKD patients. From this observation it appears that patients with altered renal function possess unique risk factors that contribute to the disease pathophysiology in this setting.

One potential, yet unproven, risk factor for the development of atherosclerosis in patients with chronic kidney disease is trimethylamine-N-oxide (TMAO). TMAO is a circulating organic compound produced by enteric microbial metabolism of dietary L-carnitine and choline (2,3) which results in formation of trimethylamine (TMA), a metabolite that is absorbed from the intestine and subsequently oxidized by hepatic flavin monooxygenase enzymes to form TMAO (6). TMAO has been observed to directly induce atherosclerosis

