in rodents and was found to be strongly associated with the incidence of cardiovascular events in humans (2-5). In normal physiologic conditions, circulating TMAO is rapidly removed from circulation primarily by excretion into the urine (7). We previously postulated that TMAO levels would be substantially elevated in patients with CKD, and to test this hypothesis we performed a cross-sectional analysis of serum TMAO concentrations in a cohort of patients with varying levels of CKD and normal healthy controls. In this study, we observed serum TMAO concentrations become markedly elevated in the advanced stages of CKD, with end-stage renal disease (ESRD) patients exhibiting mean levels 30-fold higher than healthy controls.

If TMAO contributes to atherosclerosis formation in CKD patients, therapeutic interventions to reduce TMAO production may represent a method to reduce cardiovascular morbidity and mortality in this population. Prior studies suggest that short-term suppression of gut flora with antibiotics dramatically decreased TMAO levels in patients with normal kidney function (5); however, this approach has not yet been tested in patients with CKD that exhibit much higher serum levels of TMAO.

Rifaximin is a novel antibiotic that is currently approved for treatment of hepatic encephalopathy in patients with end-stage liver disease. Rifaximin demonstrates little systemic absorption, with 97% of the parent drug being excreted unchanged in the feces (9). Its primary use is to target pathogenic intestinal bacteria in various disease states , including cirrhosis and traveler's diarrhea. In this study we seek to evaluate whether Rifaximin will decrease levels of TMAO in patients with advanced kidney disease and to study the effects of Rifaximin on the intestinal microbiome of patients with CKD.

Explain how the performance of this proposed project will advance our knowledge in this field, and/or improve our understanding of the disease or physiological condition being studied.

This study will determine if elevated levels of TMAO in CKD are at least partially dependent on the presence of certain intestinal flora and if serum TMAO levels are modifiable by therapy with Rifaximin.

3. Explain how this study might improve the diagnosis or treatment of the disease being studied (if applicable), or advance knowledge in the field.

This will provide preliminary evidence to support the intestinal flora as a target for reducing TMAO levels in CKD patients.

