Blood, urine and stool samples will be labeled with study information and by the subjects' unique study ID. They will be analyzed in the lab of [name] and the lab of [name] at the University of Pittsburgh Medical Center. Additional serum and urine samples will be stored in a -80°C freezer in [name] lab for those patients consenting for sample storage.

5. Timeline: Consider attaching a study flow chart illustrating subject visits and tests or procedures to be performed at each visit **and/or** include a chart or graph format that reflects the project activities and anticipated time frame of completion.

Day 0 (baseline visit): Consented participants will have an initial appointment dedicated to the collection of baseline samples and study medication will be dispensed at this visit. Complete review of the patient's history and physical examination will be recorded. All study participants will continue receive standard of care treatment for their chronic kidney disease. Study participants will be provided with a 10-day course of Rifaximin. A medical history will be obtained, including current medications, comorbid conditions, lifestyle indicators (such as tobacco and alcohol use), review of recent laboratory studies (such as BMP, CBC, and lipids); this information will be recorded and stored on all study participants. Serum, urine and fecal samples will be collected at this

visit. On Day 1, study participants will begin Rifaximin 550mg PO BID or placebo for a total of ten days duration.

Day 11 (post-therapy follow-up visit): Study participants will provide stool samples within 24 hours of their last dose of Rifaximin or placebo. Serum and urine samples will be drawn at this study visit. Vital signs will be checked and a brief interview will be conducted to assess for any potential adverse reactions to the study medication. Follow up visits can be arranged at the patient's request if needed.

Day 25 (steady state follow-up visit): Study participants will provide stool samples. Serum and urine samples will be drawn at this study visit. Vital signs will be checked and a brief interview will be conducted to assess any recent health changes.

- **F. Risk/benefit assessment:** As appropriate, address the following parameters as each relates to the individual subject in the study. Be sure to include consideration of study assignment (Arm A, Arm B, placebo, active substance, etc):

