- 1. Physical risk: Rifaximin has known potential side effects. Since this medication has primarily been studied in patients with advanced liver disease, it is unclear which of these side effects are unique to this population of patients. The most common side effects reported in patients with liver disease included peripheral edema, ascites, nausea, dizziness, fatigue, headache, muscle spasms, pruritus, abdominal pain, and rash. Most common side effects in patients without liver disease are believed to be gastrointestinal in nature; mainly including nausea, abdominal pain/bloating, and diarrhea. Serious reactions have been reported by the manufacturer with this therapy, including superinfection with clostridium difficile, hypersensitivity reaction, angioedema, anaphylaxis, and exfoliative dermatitis. The risks associated with venipuncture in order to obtain blood samples carries a small risk of excessive bleeding, vasovagal syncope, hematoma/infection at the site of vein puncture, and potentially multiple punctures in order to locate veins.
- 2. Psychological risk: No anticipated risk.
- 3. Social risk: No anticipated risk.
- 4. Economic risk: Low anticipated risk. The patient will have no cost associated with the study. In the instance of an adverse event, normal medical treatment should be sought and insurance billed as is standard.
- 5. Potential benefit of participating in the study:
 - a. To the individual subject and/or parent if any: Individuals are not expected to benefit directly from participation in this study.
 - b. To the population from which the subject is drawn: This study may provide critical insight into understanding the altered metabolism of TMAO in CKD and provide preliminary evidence to support the development of future large-scale studies.
 - c. To science, society, and humanity in general: This may lead to development of interventions which could decrease the burden of cardiovascular disease in patients with chronic kidney disease, ultimately reducing health care costs and outcomes for patients with these conditions.
- **G. Location where study will be performed:** Indicate where all portions of the study will take place and where the research subject's records will be kept.

This study will be conducted at the University of Kansas Hospital with patients being recruited from the outpatient nephrology clinics. Records will be kept on secure spreadsheets that can only be accessed by the study team.

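### Diet and appetite are not recorded during treatment, so a fall in TMAO is harder to attribute to flora suppression

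*Combined protocol and SAP*

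**What the plan says.** Section I.A.1 describes TMAO as "a circulating organic compound produced by the metabolism of dietary L-carnitine and choline", and section I.C.1 adds the microbial step: it is "produced by enteric microbial metabolism of dietary L-carnitine and choline". The hypothesis in I.A.2 is that rifaximin "will suppress the bacterial flora that are responsible for the generation of trimethylamine, a TMAO precursor, and subsequently reduce serum TMAO concentrations", and the primary outcome is the "change in serum TMAO concentrations (post-therapy minus pre-therapy TMAO) following Rifaximin administration for 10 days". Section I.C goes on to promise an answer on whether raised TMAO in CKD is "at least partially dependent on the presence of certain intestinal flora", and on whether the drug can modify it. The primary objective in II.A is narrower: whether ten days of rifaximin lowers serum TMAO.

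On tolerability, II.F.1 says: "Most common side effects in patients without liver disease are believed to be gastrointestinal in nature; mainly including nausea, abdominal pain/bloating, and diarrhea".

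The visit schedule in II.E.5 provides for the following:

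- **Day 0:** history, examination, medications, comorbidities, recent laboratory results, and "lifestyle indicators (such as tobacco and alcohol use" as examples of habits.
- **Day 11:** samples, vital signs and a short interview about adverse reactions.
- **Day 25:** samples, vital signs and a short interview about changes in health.

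Section II.E.2 lists sample collection only. In the text available, nothing asks participants to keep a stable diet or records food intake or appetite on treatment. The only analysis stated in V.A is a two-sided paired t-test of TMAO before and after antibiotic.

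**The concern.** Serum TMAO depends on how much precursor is eaten as well as on the bacteria that convert it. A drug that causes nausea, bloating or diarrhoea could reduce eating during the ten days just before the Day 11 sample. Some of a fall in TMAO could then come from a smaller precursor supply. Randomisation balances habitual diet at entry, but it does not remove a change in intake that the treatment itself causes afterwards.

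What is at stake is the mechanistic conclusion. The study is meant to supply preliminary evidence for the intestinal flora as a target, and intake that is not recorded at the time cannot be reliably recovered later. The human antibiotic study summarised in I.B.3 gave participants a phosphatidylcholine challenge. This design neither sets a precursor load nor measures one.

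**Working it through.** **1. The plan's own figure.** Inputs from II.C.1 and V.A: mean change -30%, SD 30%, two-sided alpha 0.05, power 90%, paired t-test. The standardised effect is 30/30 = 1. With the noncentral t distribution, n = 13 gives power 0.911, so the stated 13 is reproduced; n = 15 gives 0.949. No figure in the documents depends on diet, so the gap itself is established from the text.

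**2. How large could a diet-only difference be?** The documents give no gastrointestinal event rates and no effect on intake. Three assumptions are needed:

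- Serum TMAO is proportional to precursor intake.
- The excess share of participants with symptoms, rifaximin minus placebo, is 0.10 to 0.30.
- Those participants cut intake by 0.25 to 0.50.

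Diet-only difference = excess share × relative cut:

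| Excess share | Cut 0.25 | Cut 0.50 |
|---|---|---|
| 0.10 | 2.5% | 5% |
| 0.30 | 7.5% | 15% |

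Against the planned 30%, this runs from 2.5/30 = 0.08 to 15/30 = 0.50.

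**3. Could that alone give a significant result?** Take no flora effect, SD 30%, and a mean fall in the rifaximin arm only. The probabilities of p < 0.05 are:

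| Mean fall | Paired, n = 15 | Between arms, 15 vs 15 |
|---|---|---|
| 0% | 0.05 | 0.05 |
| 5% | 0.09 | 0.07 |
| 10% | 0.23 | 0.14 |
| 15% | 0.44 | 0.26 |

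**4. Smallest observed fall that reaches p < 0.05, at SD 30%.**

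- Paired: 2.145 × 30/√15 = 16.6%.
- Between arms: 2.048 × 30 × √(2/15) = 22.4%.

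Even the extreme corner of step 2 lies below both thresholds, although sampling variation could carry an observed fall past them.

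**The case against.** A reader might infer that the primary result is biased, or that the data could not distinguish reduced eating from flora suppression at all. The documents support neither.

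- **Primary objective.** II.A asks whether rifaximin lowers serum TMAO. Lower intake caused by the drug is part of that total effect and does not bias it. This stands in full, provided the arms are compared.
- **Evidence on mechanism.** Stool is collected at Days 0, 11 and 25, and change in microbiota is a secondary aim. The Day 11 interview may pick up nausea or diarrhoea, so TMAO change in participants without symptoms could be examined. This stands in part. Stool data show whether flora changed, not how much of the TMAO fall that explains, and the mouse study cited in I.B.3 found that L-carnitine feeding itself altered gut bacteria. The interview does not measure intake. A rebound at Day 25 would not settle the matter either, because appetite could return once dosing stops.
- **Open list at Day 0.** The examples of habits are only examples, and diet could be included. True, but a baseline entry cannot show change on treatment.
- **Assumed chain.** II.F.1 gives no rates and no placebo comparison, and does not say that patients eat less. Proportionality ignores clearance, although I.C.1 says TMAO leaves mainly in urine. This stands: the size is unknown.
- **Limits of adjustment.** An excess of 10 to 30 points is 1.5 to 4.5 of 15 participants. Excluding or adjusting for them conditions on a post-randomisation variable in a very small sample. This also stands, and it shapes the fix.

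**Conclusion.** The concern holds as a limit on interpretation. The protocol names diet as the source of TMAO and gastrointestinal effects as common, but records nothing about intake or appetite at Days 11 and 25 and does not ask for a stable diet. The total effect of rifaximin remains estimable from a between-arm comparison. Attribution to flora, as framed in I.A.2 and I.C, is weaker than it need be.

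Under the stated assumptions the dietary contribution is 2.5 to 15%, at most half of the planned 30%. Diet alone would therefore not account for a fall of the planned size within that range. The range rests wholly on assumed inputs. One part of section II, between the study location and the safety monitoring plan, was not available to check.

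**What to change.** **II.E.5.** At Day 0, ask participants to keep their usual diet until Day 25. At Days 0, 11 and 25, add a short recall with fixed questions and a fixed look-back period, covering the main L-carnitine and choline sources, loss of appetite and skipped meals. Amend II.E.2 to match.

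**V.A.** Compare TMAO change between arms as randomised; the current text states only a before-and-after test. Report change in intake and gastrointestinal symptoms descriptively by arm. Label any analysis restricted to or adjusted for intake as exploratory.

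**Cost.** About 5 to 10 minutes at each of three visits that already include a history or interview, plus one table. Recall is imprecise. The between-arm comparison is also less powerful than the paired test: with 15 per arm, a 30-point difference and SD 30% in both arms, power is 0.75, and 90% would need 23 per arm. In a pilot of 30 the result is best given as an estimate with a confidence interval.

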- 1. Please note that any study proposal with more than minimal risk must include a data and safety monitoring plan. Elements of the plan include:
 - a. Persons/groups who will review the data (study team; independent safety monitor, data monitoring committee or formal DSMB)
 The study team
 - b. Data/events that will be reviewed
 Adverse reactions, early discontinuation, tolerance and side effects.
 - c. Frequency of review

 After ten days of therapy and PRN.
 - d. Types of analyses to be performed Patient interview
 - e. Safety-related triggers that would cause the PI to stop or alter the study Multiple adverse reactions may lead the team to reconsider the dose or the chosen agent.
- 2. Describe how adverse events and unanticipated problems will be ascertained and handled. Explain exactly which type of problems will be considered serious and reported to the IRB. The reporting timeframe should also be detailed.

Participants will be given contact information for KU nephrology on-call numbers. There have been rare serious adverse medication reactions with Rifaximin, including intestinal

superinfection, C-diff associated diarrhea, angioedema, or exfoliative dermatitis. In these instances a patient will be instructed to seek emergency medical attention.

3. Explain exactly what will happen if a patient experiences an adverse event or other problem (for example, will discontinue study participation).

Patients will be asked to report any adverse reaction. They will be given the contact information for the nephrology nursing line who can contact a member of the study team. This is a short study lasting 25 days and patients will have 3 total study visits, on day 0, day 11, and day 25.

III. Subject Participation

A. Recruitment:

1. Describe locations from which the subjects will be recruited and what arrangements have been made with other institutions (if applicable).

The initial contact will occur at KU nephrology clinic. There will not be outside institutions involved.

2. Describe by whom and how the recruitment is conducted.

A subject's primary treatment team will be the initial contact to gauge interest in learning about the study. From there a member of the study team will discuss the study in further detail.

3. Attach a copy of advertisements and/or flyers and state where they will be placed.

There will not be advertisements or flyers.

4. Attach a copy of the recruitment letter or introductory statement and describe planned use or distribution of the document.

There will not be a recruitment letter.

B. Screening Interview/questionnaire: If an interview or questionnaire will be used for screening, attach a copy and indicate where, how, and who will conduct the interviews and their qualifications. Address how consent to participate in the screening process will be obtained.

Clinic patients will be screened for inclusion and exclusion criteria. If they are appropriate for inclusion in the study they will be approached by their clinical nephrology team members who will assess their interest and willingness to participate in the study. If they are interested in participation a member of the study team will discuss the study in further detail.

C. Informed consent process and timing of obtaining of consent

1 Indicate who will give subjects detailed and comprehensive information about the study and obtain their written consent.

A member of the study team as outlined above.

2 Indicate how the consenting process will be structured to ensure independent and thoughtful decision-making, and what steps will be taken to avoid coercion and guarantee confidentiality.

Clinic patients will be screened in advance for inclusion and exclusion criteria. During their clinic visit with their clinical nephrologist, their doctor will ask if they are interested in participating in the study. If the patient expresses interest, a member of the study team will discuss the project with the patient. The consent may be obtained at that clinical visit if time permits for full explanation and patient is agreeable. Alternatively they may take the consent form home for review and a study visit will be arranged at a separate time and location.

Indicate how, and by whom, it will be determined whether the subject is able to give informed consent, or whether their legal guardian will give informed consent. For subjects whose ability to give informed consent may be compromised by cognitive and/or decisional impairment (examples may include individuals with a psychiatric disorder, an organic impairment, a developmental disorder, or those suffering from a terminal illness, degenerative disease, severe physical handicap or dependence on drugs or alcohol), complete Appendix I.

A member of the study team will determine if a subject is able to consent for the study. This study will not involve patients under the age of 18, pregnant patients, or those who are unable to provide consent.

D. Alternatives to Participation: A statement of alternatives to participation in this research study, if any.

Subjects may choose not to participate in the study. This will not affect their ability to receive care at KU.

E. Costs to Subjects: Indicate what will happen if the subject's insurance company refuses to pay for costs of clinical care when those tests are also used for research purposes. Indicate what will happen if the study subject does not have insurance.

Patients will not incur costs associated with this study.

F. How new information will be conveyed to the study subject and how it will be documented: Articulation of how new information will be conveyed to the study subject and how it will be documented.

Patients will be informed at the time new information is recognized. This will likely be conveyed during a research appointment but if urgent a phone call will be initiated.

G. Payment, including a prorated plan for payment: Indicate how much subjects will receive for each portion of the study and the reimbursement schedule to be used if the subject withdraws or is withdrawn during the study. Indicate if travel costs be reimbursed.

Subjects will not receive payment for participation.

H. Payment for a research-related injury: Information regarding payment for a research-related injury.

Patients will be directed to standard medical care in the event of an adverse reaction and their insurance will be billed accordingly.

IV. Data Collection and Protection

- A. Data Management and Security: Describe how data will be collected and protected
 - 1. State the persons/groups who will have access to study data.

Only members of the study team will have identifying information. Information will be de-identified before analysis.

2. Discuss procedures for maintaining subject confidentiality, any special data security requirements, and record retention per the university policy.

All records relative to the research will be treated in confidence, with hard copies of consent forms stored in a locked office in the Kidney Institute. Study spreadsheets will be maintained on secure drives that can only be accessed by study members and agents of the University or federal government who oversee research involving human subjects.

- 3. State whether human subjects will be identifiable directly or through coded information.
 - Subjects will be assigned a unique study ID.
- 4. If data will be coded, state who will maintain and have access to the key to the code.

Only Members of the study team will have access to identifiable study information.

5. State how the data will be linked to the subjects during the study.

By means of a unique study ID. Master sheet linking patients with their ID's will be stored on secure drive as noted above and maintained by the lead study coordinator.

6. State how and where the data will be stored, and how it will be protected.

All records relative to the research will be treated in confidence and stored in the Kidney Institute. Electronically stored information will be maintained on a secure server.

7. Discuss any use of mobile devices for data collection or storage.

Mobile devices will not be used for study collection or storage.

8. Discuss security measures if identifiable data are sent outside KUMC.

Only de-identified information will be sent outside KUMC.

B. Sample / Specimen Collection: Describe how samples will be collected at each site. Include how they will be stored, protected, and shared, as applicable. Include length of storage.

Serum and urine samples will be collected on day 0 (prior to antibiotic administration), day 11 and day 25. Patients will be asked to provide a stool sample for future microbiome analysis prior to their baseline visit and within 24 hours of each study visit. The specimens will be labeled with the study ID. Unless consent for long-term blood and urine storage has been obtained, the samples will be destroyed after testing. A separate consent form will be provided for optional blood and urine storage for future testing. Samples will be stored in a -80°C freezer in [name] lab for those patients consenting for sample storage.

C. Tissue Banking Considerations: If samples will be banked for future use, describe the purposes of the future use, how samples will be labeled and with whom they will be shared. Seek further guidance from the IRB if you are creating a repository.

Samples will be labeled with the study information and the participants unique study identification. Samples may be used in further studies involving chronic kidney disease.

D. Procedures to protect subject confidentiality: Identify any part of the study that may place subject confidentiality at risk. Describe study procedures to protect subject confidentiality.

The researchers will only use and share information that is needed for the study. Identifying information collected may include such information as name, address, phone, date of birth, or other identifiers. Participants health information will be reviewed at KUMC by [name], members of the research team, The University of Kansas Hospital Medical Record Department, the KUMC Research Institute and officials at KUMC who oversee research, including members of the KUMC Human Subjects Committee and other committees and offices that review and monitor research studies. Data will be de-identified prior to analysis and prior to outside involvement in the study.

E. Quality Assurance / Monitoring

1. Describe steps to be taken to assure that the data collected are accurate, consistent, complete and reliable. (source data verification, audits or self – assessment)

Self-assessment.

2. Describe whether there are plans to have ongoing third party monitoring.

There is no plan for third party monitoring.

V. Data Analysis and Reporting

A. Statistical and Data Analysis: A description of the statistical methods to be employed in data analysis, including timing of any planned interim analysis

The study will be considered complete when the necessary power is obtained. A paired, two-sided Student's t-test will be used to compare differences in pre-antibiotic and post-antibiotic TMAO levels.

B. Outcome: Describe what results are expected, the criteria for success or failure and the end point of the study.

We expect that our intervention will lead to significant short-term reductions in serum TMAO levels.

C. Study results to participants: List any study results to be given to subjects and indicate how, when and why they will be given.

Study findings may be discussed at the conclusion of the study by participant request.

D. Publication Plan: Describe plans for publication of research results.

Results may be published in abstract form or as part of a peer-reviewed original research manuscript.

- **VI. Bibliography / References / Literature Cited** (choose the applicable title and list citations according to APA or other accepted style in your discipline)
